Official Title: Development and Preliminary Examination of Two Brief Personalized Feedback Interventions Focused on Lab-based and EMA Alcohol Cues to Reduce Hazardous Young Adult Alcohol Use

Brief Title: Testing Brief Personalized Feedback Integrating Lab-based Alcohol Cue Information (Project ACE)

NCT number: NCT05873556

Document date: February 15, 2025

STUDY PROTOCOL

Given the role of cue reactivity in eliciting alcohol-related cravings that can lead to increased alcohol use, the current study develops and tests a novel intervention strategy that may ultimately increase the strength of Personalized Feedback Intervention (PFI) effects to reduce young adult alcohol misuse. We developed a novel Cue Reactivity PFI based on an *in vivo* cue reactivity session that includes personalized feedback regarding the extent to which young adults' desire to drink varied in response to an alcohol cue (i.e., alcoholic beverage of their choice) presented during a lab session. We anticipate that this feedback will increase young adults' awareness of their drinking, consequences, and cues that may increase their desire to drink. The intervention aims to equip young adults with strategies for reducing exposure to factors that increase their desire to drink, how to cope with an increased desire to drink, and how to reduce potential harms from drinking.

The study design is a randomized clinical trial that includes an in-person *in vivo* cue reactivity session at the study office and online baseline, 2-week, and 3-month surveys. Participants are randomized to either a PFI condition or an assessment-only condition. The study tests initial development of the PFI intervention, which is in the form of personalized feedback and is delivered online to the intervention group. All participants complete the cue reactivity session and baseline, 2-week and 3-month surveys.

Individuals who agreed to participate in the screening survey (Information Statement presented) and who were eligible based on the screening survey were contacted by research staff to verify their identity (e.g., name, date of birth). Participants were then sent a link to complete the informed consent process (Consent Form) and baseline survey. In the baseline survey, participants identified their preferred beverage from a list of alcoholic beverages that are commonly consumed by young adults and that cover a range of alcohol types (e.g., beer, wine). After participants completed the baseline survey, they were scheduled for an in-person *in vivo* cue reactivity session with a research staff member.

All participants complete the lab-based cue reactivity protocol that involves an *in vivo* alcohol cue exposure task. At the start of the lab session, participants were randomized to either a cue reactivity PFI condition or assessment-only condition. In the lab session, participants first confirmed their identity by showing either a drivers license or ID card. To enhance the personalization of the cues, the cue reactivity protocol for each participant involves exposure to their preferred alcoholic beverage. During the lab session, participants complete a series of questionnaires, both before and after the cue exposure. Participants undergo a 3-minute block in which they are instructed (by audio delivered via headphones) to hold and smell a glass of their preferred alcoholic beverage. Participants follow the audio-taped instructions about picking up and smelling the beverage.

After the cue reactivity protocol, participants in the control condition complete several additional questionnaires to increase comparability of session time. Participants in the PFI condition view the online personalized feedback and complete a brief survey to assess reactions to their feedback. Intervention participants are also emailed a link to their personalized feedback so the participant can view it again after the lab session. The personalized feedback consists of pre-programmed content viewable on either a computer or mobile phone. The personalized feedback uses participants' responses from the baseline survey and from the lab-based cue reactivity protocol. The aim of the intervention is to increase young adults' awareness of how alcohol cues may affect their desire to drink, mood, willingness to drink, and alcohol demand both in relation to lab-based exposure to an alcohol beverage of their choice and also more broadly in everyday life.

Official Title: Development and Preliminary Examination of Two Brief Personalized Feedback Interventions Focused on Lab-based and EMA Alcohol Cues to Reduce Hazardous Young Adult Alcohol Use

Brief Title: Testing Brief Personalized Feedback Integrating Lab-based Alcohol Cue Information (Project ACE)

NCT number: NCT05873556

Document date: February 15, 2025

STATISTICAL ANALYSES

Prior to any inferential statistics, univariate and bivariate descriptive statistics will be used to assess distributions for baseline data and 2-week and 3-month follow-up data. Given the repeated measures design, generalized linear mixed models (GLMM; Raudenbush & Bryk, 2002) will be used. GLMM (aka hierarchical generalized linear models) allow for non-normal outcomes and missing data, handle varying time-points, and accommodate time-varying and time-invariant covariates. Separate models will test for intervention effects on craving, alcohol use, and consequences. Hypotheses compare the Cue Reactivity PFI to the assessment-only control (AOC). Models include three repeated measures (baseline, 2-week, 3-month) where Level 1 refers to repeated-measures and Level 2 refers to people. To determine whether the EMA-based PFI is associated with reduced drinking and negative consequences at the follow-ups, we will use Poisson forms of regression models, which are appropriate for count outcomes. The following equations represent the basic analytic model and serve as the basis to test intervention effects with drinking as an example:

```
Level 1: \log(\text{E}[\text{Alcohol}_{ti}]) = \pi_{0i} + \pi_{1i}(\text{Time1})_i + \pi_{2i}(\text{Time2})_i + \varepsilon_{ti} \varepsilon_{ti} \sim N(0, I\sigma_{\varepsilon}^2)

Level 2: \pi_{0i} = \beta_{00} + \beta_{01}(\text{Intervention Condition})_i + r_{00i}

\pi_{1i} = \beta_{10} + \beta_{11}(\text{Intervention Condition})_i + r_{10i}

\pi_{2i} = \beta_{20} + \beta_{21}(\text{Intervention Condition})_i + r_{20i}
```

where t indexes repeated-measures and i indexes participants. $Alcohol_{ii}$ represents the outcome measured at each time point for each individual. Time will be coded as two dummy variables that compare the 2-week (Time1) and 3-month (Time2) follow-ups to baseline (reference category). Intervention Condition will be a dummy variable to compare the PFI condition to the AOC condition (reference). Of particular interest are parameters that reflect the interaction between intervention condition and Time (e.g., β_{21} at 3-month). For count outcomes, the outcome is connected to covariates through a log link function, which is the standard link function for Poisson GLMM. Covariates can be exponentiated to yield Rate Ratios (RRs) that describe the proportional change in the count outcome associated with a 1-unit increase in the covariate. If data show over-dispersion where the variance exceeds the mean, the model will be extended to include a scale parameter to fit an over-dispersed Poisson, or we will consider zero-altered models to ensure accurate inferences (Atkins et al., 2013; Atkins & Gallop, 2007). We will also consider adding baseline covariates to improve precision or if evidence suggests an imbalance in the distribution of the covariate(s) across conditions.

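### Does the SAP need a primary contrast or a multiplicity rule for three outcomes at two follow-ups?

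*SAP*

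**What the plan says.** The SAP (Statistical Analyses) names three outcome domains: "Separate models will test for intervention effects on craving, alcohol use, and consequences". The comparison is a single one between two arms: "Hypotheses compare the Cue Reactivity PFI to the assessment-only control (AOC"). On time, "Time will be coded as two dummy variables that compare the 2-week (Time1) and 3-month (Time2) follow-ups to baseline (reference category"), so each outcome has a 2-week interaction (β11) and a 3-month interaction (β21). These interactions are the target of inference: "Of particular interest are parameters that reflect the interaction between intervention condition and Time". The 3-month coefficient follows as an instance of the type, and the model equations likewise "serve as the basis to test intervention effects with drinking as an example". Neither passage selects a primary test.

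The SAP also leaves the count model partly open. If the data are over-dispersed, one option is that "we will consider zero-altered models to ensure accurate inferences". No significance level, order of testing, joint test or multiplicity adjustment appears in either document.

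On the stage of the work, the Protocol says that "The study tests initial development of the PFI intervention", and the official title of both documents describes the examination as preliminary.

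**The concern.** Three outcomes by two follow-ups give six interaction terms, or three tests if each outcome gets one joint 2-df test. The SAP does not say which. It uses the language of hypotheses and testing and does not call the results exploratory. A reader holding only these documents could see one significant term out of six reported as evidence of benefit and have no stated rule to set against that reading. The alcohol-use measure is not defined, and a zero-altered model can carry a condition-by-time term in each of two parts. So even the 3-month drinking contrast is not yet one test, and six may undercount.

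At stake would be a false claim of efficacy, at a rate above the usual 5%, for an intervention that might then go on to a larger trial.

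**Working it through.** There is no error rate in the documents to reproduce, so the check is of scale only.

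**Inputs from the SAP:** 3 outcomes and 2 follow-up contrasts per outcome, so 3 × 2 = 6 terms.

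**Assumptions, not in the documents:** two-sided 0.05 per test; all null hypotheses true; any one significant term counts as success; correlations between test statistics from 0 to 0.9.

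**Uncorrelated tests, exact:**
- Any of six significant: 1 − 0.95^6 = 0.265.
- Any of six significant in favour of the intervention: 1 − 0.975^6 = 0.141, against 0.025 for one test.
- Three joint 2-df tests: 1 − 0.95^3 = 0.143.

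**Correlated tests**, by multivariate normal simulation with an outcome-by-time product correlation:

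| Correlation between outcomes / between times | Any of six | Any of six, favouring intervention | Any of three joint tests |
|---|---|---|---|
| 0 / 0 | 26.5% | 14.1% | 14.3% |
| 0.3 / 0.5 | 23.8% | 12.0% | 13.7% |
| 0.5 / 0.6 | 21.2% | 10.6% | 12.7% |
| 0.7 / 0.7 | 17.7% | 8.8% | 11.1% |
| 0.8 / 0.8 | 14.9% | 7.4% | 10.0% |
| 0.9 / 0.9 | 11.6% | 5.8% | 8.5% |

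If every pair is correlated 0.9, the six-test figure is 10.8%; hence about 11-12% at the low end. The uncorrelated row is implausible, because the two interactions for one outcome share the same participants and the same baseline.

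**What a formal rule would cost.** Take contrasts with an assumed 80% power at 0.05, that is, a true effect of 1.960 + 0.842 = 2.802 standard errors.
- Holm over all six: the strictest step is 0.05/6 = 0.0083, where power is 56.5%.
- One primary at 0.05, with the other five tested by Holm only if it succeeds: the first step is 0.05/5 = 0.01, where power is 58.9%. With uncorrelated tests, passing the gate as well gives about 0.80 × 0.589 = 0.47. By simulation the range is 47% (0 / 0) to 57% (0.8 / 0.8), when the primary also has 80% power and the other four contrasts are null.

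**What a formal rule would secure.** Six independent tests at 0.05/6 give 1 − (1 − 0.05/6)^6 = 4.9%. That holds only if there are exactly six tests. Suppose both count outcomes were fitted with independent two-part models and either part could be claimed. The count is then 2 outcomes × 2 times × 2 parts + 2 craving terms = 10, and 1 − (1 − 0.05/6)^10 = 8.0%. Adjusting over six would not by itself deliver 5%.

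**The case for a change.** The best case for requiring a change is that it would cost almost nothing. One or two sentences would either name a primary contrast or label all six exploratory, and a reader could then tell a planned positive result from the best of several. Preliminary status lowers the stakes but does not supply the missing rule. The SAP refers to hypotheses, and nothing in it prevents a single significant term from being presented as success. Correlation among the tests shrinks the excess without removing it.

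Much of this stands. The ranking is absent, the arithmetic is right, and a lone significant term among six deserves discounting. Three things weaken the demand for a change.

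- The 26.5% is not a property of the plan. It needs a rule that any one significant term counts as success, and the documents contain no such rule.
- The plan does disclose the family. Outcome domains, follow-ups, comparator and type of parameter are all listed, so a reader can count the planned terms and weigh a lone positive accordingly.
- Naming a primary contrast now may secure little. The Protocol already reports allocation in the past tense: "At the start of the lab session, participants were randomized to either a cue reactivity PFI condition or assessment-only condition". Outcome data may therefore exist, and if they have been examined by arm, a choice made afterwards would not hold the error at 5%.

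**Conclusion.** No change to the plan follows. This is an unwritten rule in a study that presents itself as preliminary and states no significance level, success criterion or error-rate guarantee that the six tests could breach. The lightest remedy, an exploratory label, is one that even the concern accepts as a full answer, and it would leave every model, estimate and test as it is. The heavier remedy, a gated or Holm procedure, would cut a secondary contrast from 80% to about 47-57% power under the assumptions shown. Reasonable statisticians differ on whether that is worth paying at the development stage.

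The size of the issue, if any one significant term were taken as success, is 26.5% falling to about 11-12% two-sided, or 14.1% falling to 5.8% in the intervention's favour. Both rest on an assumed two-sided 0.05, all nulls true and exactly six tests; more tests, as under two-part models, would raise them. Analysts would ordinarily fill the gap by reporting all six contrasts with confidence intervals and treating an isolated significant one as a lead for a later trial. The judgement would differ if the documents made a confirmatory claim of efficacy or stated an overall error rate. They do neither.

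### The models estimate a free baseline arm difference, so the condition-by-time effects are less precise than the baseline survey already collected would allow

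*SAP*

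**What the plan says.** The SAP (Statistical Analyses) says: "Separate models will test for intervention effects on craving, alcohol use, and consequences". On the occasions used: "Models include three repeated measures (baseline, 2-week, 3-month"). On coding: "Time will be coded as two dummy variables that compare the 2-week (Time1) and 3-month (Time2) follow-ups to baseline (reference category"). The Level 2 intercept equation lets the arms differ at baseline: "\pi_{0i} = \beta_{00} + \beta_{01}(\text{Intervention Condition})_i + r_{00i"}. The target is the interaction: "Of particular interest are parameters that reflect the interaction between intervention condition and Time". On covariates, the SAP adds: "We will also consider adding baseline covariates to improve precision". It names none and does not say how they would enter.

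The protocol gives the order of events. Participants complete the baseline survey online and are then scheduled for the lab session, where randomisation takes place at the start. In both arms, "During the lab session, participants complete a series of questionnaires, both before and after the cue exposure". The arms are handled differently only later: "After the cue reactivity protocol, participants in the control condition complete several additional questionnaires to increase comparability of session time". Those in the feedback condition view their feedback at that stage. The SAP does not mention the lab ratings.

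**The concern.** With β01 free, β11 and β21 are differences between arms in change from baseline. All the sampling noise in the observed baseline arm difference is carried into the effect estimate. Randomisation comes after the baseline survey, so that difference is known to be zero in expectation and need not be estimated. Baseline can instead be used to predict follow-up, which never does worse in large samples under equal variances and does clearly better at moderate correlations.

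Interval width is what is at stake. The trial is described as a preliminary examination, and its main product is an estimate with an interval. A wider interval than the data require weakens what can be said about whether the feedback merits further testing.

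**Working it through.** **Inputs from the documents.** One pre-treatment occasion enters each model; β01 is free; β11 and β21 are the targets; baseline precedes randomisation. The documents give no sample size, power, standard deviation or correlation, so there is no figure of the plan's own to reproduce.

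**Assumptions.** Linear model, complete data, equal variance σ² at each occasion and in each arm. B is the baseline survey, Y a follow-up, and r their correlation, taken as 0.3, 0.5 and 0.7. Per-person variances are in units of σ². The number per arm cancels in the ratios.

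1. β01 free: the contrast compares mean Y − B between arms. Variance = 1 + 1 − 2r = 2(1 − r).
2. β01 set to zero, or B used as a covariate: variance = 1 − r².
3. Ratio = (1 − r²) / [2(1 − r)] = (1 + r)/2, which is below 1 for any r below 1.

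The last column is a translation only. It assumes that the SAP model has 80% power at two-sided 0.05 and computes Φ(2.802/√ratio − 1.960).

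| r | 2(1 − r) | 1 − r² | variance ratio | SE ratio | 80% power becomes |
|---|---|---|---|---|---|
| 0.3 | 1.40 | 0.91 | 0.65 | 0.81 | 93.5% |
| 0.5 | 1.00 | 0.75 | 0.75 | 0.87 | 89.9% |
| 0.7 | 0.60 | 0.51 | 0.85 | 0.92 | 86.0% |

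A ratio of 0.75 is worth 1/0.75 = 1.33, or about a third more participants.

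**What a pre-cue lab rating L could add.** Write rLB and rLY for its correlations with baseline and follow-up.

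- In the SAP's own model (β01 free), a rating-by-time term cuts variance by (rLY − rLB)² / [2(1 − r)]. If rLY = rLB the cut is exactly zero. At r = 0.5, a gap of 0.1 gives 0.01/1 = 1% and a gap of 0.2 gives 0.04/1 = 4%.
- Over a baseline-adjusted contrast, the extra cut is (rLY − r·rLB)² / [(1 − r²)(1 − rLB²)]. If all three correlations equal r, this is [r/(1 + r)]²: 5%, 11% and 17% at 0.3, 0.5 and 0.7.
- If L is a different instrument (r and rLB each 0.4 to 0.6, rLY 0.3 to 0.5), the extra cut runs from 0 (r = 0.6, rLB = 0.5, rLY = 0.3, since 0.3 − 0.6 × 0.5 = 0) to (0.5 − 0.16)²/(0.84 × 0.84) = 0.1156/0.7056 = 16% (r = rLB = 0.4, rLY = 0.5).

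At r = 0.5, baseline adjustment takes the relative variance from 1.00 to 0.75. Adding L then gives 0.667 if all correlations are 0.5, but only 0.747 if rLY = 0.2 and rLB = 0.5. Most of the gain needs no lab data.

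**The form of entry matters.** Adding the lab visit as a fourth occasion with its own free condition term leaves the variance of β21 at 1.00. Averaging L with B gives 1 + (1 + rLB)/2 − (r + rLY). With r = 0.5, rLB = 0.5 and rLY = 0.2 that is 1.05, worse than not using L.

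**The case against.** A repeated-measures model with a free baseline term is common and gives an unbiased contrast. The SAP also leaves room for covariates to improve precision and says that its models accommodate them. The documents give no correlation, and if r is high the gain is small. The drinking and consequences models are Poisson with a log link, so the ratios above are approximate for them.

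The validity point stands: nothing here makes the planned test wrong. The approximation and the unknown r also stand, which is why a range is given. The covariate clause does not answer the point. It is optional, and a covariate with one coefficient common to all waves cancels from change over time in the linear case. Nor does it remove β01.

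A reader might go further and infer that leaving out the lab ratings costs 5% to 17% of variance in all three outcome models. The documents do not support that:

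- Those percentages apply only once the contrast is baseline-adjusted. In the model as written, the same equal-correlation assumption gives zero.
- The protocol supports a lab rating of desire to drink, because the feedback reports how desire varied with the cue. It does not name the instrument or say that it matches the craving outcome.
- No pre-cue alcohol-demand score is established. Demand appears in a statement of what the feedback aims to address, and that feedback also draws on the baseline survey. Nor is a screening drinking count established.
- The ratings follow randomisation, and the documents do not say who knew the allocation when they were given.

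**Conclusion.** The point holds as a loss of efficiency in β11 and β21 for all three outcomes, caused by estimating a baseline arm difference that randomisation makes unnecessary. The variance ratio available from baseline adjustment is (1 + r)/2: 0.65 to 0.85 for assumed r of 0.3 to 0.7. It rests on linearity, complete data and equal variances, and is only indicative for the Poisson models. No bias or invalid inference is shown.

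The lab rating is a secondary matter, for craving only. Its further gain depends on correlations that the documents do not give and may be nil. It is a safe covariate only if allocation could not have influenced it. For alcohol use and consequences, the documents give no basis for a lab-derived covariate. This is a worthwhile improvement, not a defect that must be repaired.

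**What to change.** 1. In the SAP, obtain the arm contrasts with baseline adjusted for, in one of two ways fixed in advance. Either keep the three-occasion model and set β01 to zero, so that the arms share a baseline mean and β11 and β21 are the arm contrasts at each follow-up; or model the two follow-ups only, with the baseline outcome as a covariate whose coefficient may differ by wave. Apply this whatever the observed balance.
2. For craving only, ask the sponsor to confirm whether participants, and the staff running the session, knew the allocation when the pre-cue desire-to-drink rating was given. If neither did, add that rating with a separate coefficient at each follow-up wave, alongside the baseline adjustment. If this cannot be confirmed, leave it out. Do not use post-cue ratings, do not average the rating with baseline, and do not add the lab visit as an occasion with its own free condition term.
3. Do not add an alcohol-demand or screening covariate to the alcohol-use and consequences models on the strength of these documents.

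The first change costs SAP wording only: it removes a parameter or moves baseline to the right-hand side, and needs no new data. The second costs one query to the sponsor and one coefficient per wave. Both should be fixed before outcomes are examined by arm.

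### Does naming an EMA-based PFI in the SAP's Poisson sentence detach the drinking and consequences tests from the randomised comparison?

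*SAP*

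**What the plan says.** The SAP (Statistical Analyses) plans separate models for craving, drinking and consequences, and states the comparison for them: "Hypotheses compare the Cue Reactivity PFI to the assessment-only control (AOC". Two sentences later it assigns Poisson regression to the count outcomes, opening with "To determine whether the EMA-based PFI is associated with reduced drinking and negative consequences at the follow-ups". The equations follow, with drinking as the worked example. The condition term is then defined: "Intervention Condition will be a dummy variable to compare the PFI condition to the AOC condition (reference". The tests are identified as well: "Of particular interest are parameters that reflect the interaction between intervention condition and Time".

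The protocol describes two arms. In its design paragraph, "Participants are randomized to either a PFI condition or an assessment-only condition". In its account of the lab session, "participants were randomized to either a cue reactivity PFI condition or assessment-only condition". On the content of the intervention it says "The personalized feedback uses participants' responses from the baseline survey and from the lab-based cue reactivity protocol". It describes no EMA data collection, EMA feedback or EMA arm. Apart from the one SAP sentence, EMA appears only in the official title, which covers two interventions. The brief title mentions only the lab-based one.

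**The concern.** The SAP names two different interventions within one paragraph, and the one attached to drinking and consequences is not given to anyone in this trial. That sentence is where consequences are named as a Poisson outcome, and it leads directly into the equations, so it is not background text. The later definition of the condition term speaks only of the PFI condition and does not say which PFI. Because the official title refers to both a lab-based and an EMA-based intervention, a reader could take the label as intended.

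Two things would be at stake if it were. First, the Cue Reactivity PFI would have no stated count analysis for two of its three outcomes. Second, the wording might seem to permit bringing in participants from a separate EMA study. They were not part of this randomisation, so the comparison would no longer be a randomised one.

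**Working it through.** There is no figure to reproduce. The documents give no sample size, power or effect size that bears on the point, and the issue is one of wording. The check is to set each element that defines the test beside the randomised arms.

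1. **Arms.** The protocol randomises to two conditions, the cue reactivity PFI and assessment only. Its design paragraph and its lab-session paragraph agree.
2. **Intervention content.** The feedback draws on the baseline survey and the lab session. There is no EMA source, so the only PFI in the trial is the cue reactivity one.
3. **Hypotheses.** The SAP lists the three outcomes and, in the next sentence, states the comparison as Cue Reactivity PFI against assessment-only control. Nothing limits that comparison to craving, so it covers all three outcomes.
4. **Model.** Level 2 has one condition variable, which enters the intercept (β01), the 2-week change (β11) and the 3-month change (β21). It is a dummy with the assessment-only control as reference. It takes two values, which leaves no place for a second PFI.
5. **Tests.** The parameters of interest are the condition-by-time interactions, β11 and β21. Each compares the two randomised arms on change from baseline.
6. **The sentence itself.** Its opening clause states a purpose and carries the wrong label. Its main clause selects Poisson regression for counts and does not depend on the label. For drinking, the log-link equation and the later paragraph on count outcomes supply the same choice independently. For consequences, this sentence alone names the outcome as a count, but the contrast still comes from items 3 to 5.

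**How far the label reaches.** Three outcomes at two follow-ups give 3 × 2 = 6 condition-by-time contrasts. Drinking and consequences account for 2 × 2 = 4 of them. If EMA-based PFI is read as Cue Reactivity PFI, the equations, the dummy coding, β11 and β21 all stand exactly as written. The number of contrasts whose definition changes is 0 of 6.

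**Pooling.** Neither document mentions EMA-PFI participants, a third arm or a combined data set.

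**The case for a change.** The best case for acting is that the error is certain and sits in current SAP text. It touches the sentence governing two of three outcomes and would cost one phrase to correct. The condition dummy does not say which PFI it represents, the official title gives the wrong label some plausibility, and the SAP has no sentence defining its analysis set. Anyone tracing a published result back to the SAP should find one intervention named for each test.

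The factual part of this stands: the label is wrong, and it contradicts both the SAP's hypothesis sentence and the protocol. The inference drawn from it does not. The dummy needs no further label when only one PFI is randomised. A count analysis for the Cue Reactivity PFI does exist, in the equations and their coding, and it seems absent only if one clause is read apart from the text around it. Pooling is a possibility that the documents do not raise, and silence about an EMA study is not a plan to use its data. The lack of an explicit analysis-set statement is a separate matter, which this sentence neither creates nor settles.

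**Conclusion.** The sentence contains a clerical slip and no change to the plan follows. The comparison is fixed by the hypothesis sentence, the binary condition term and the condition-by-time interactions, and all three agree with the two randomised arms. Reading the label correctly alters none of the six contrasts and no result, so an amendment would bring no inferential gain.

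This rests on two assumptions: that the analysis uses the participants randomised in this trial, which is what the condition coding implies, and that no EMA arm exists beyond what the documents describe. The wrong label may have been carried over from the second intervention in the official title. The documents do not confirm that, and the conclusion does not depend on it.

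### Baseline is modelled as an outcome with a free arm difference although the survey precedes randomisation; the effect estimate is valid but less precise than it need be

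*SAP*

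**What the plan says.** In the SAP (Statistical Analyses), baseline belongs to the outcome vector: "Models include three repeated measures (baseline, 2-week, 3-month) where Level 1 refers to repeated-measures and Level 2 refers to people". Time enters as two dummies with baseline as the reference, and the intercept equation carries a condition term: "\pi_{0i} = \beta_{00} + \beta_{01}(\text{Intervention Condition})_i + r_{00i". With that coding, beta01 is exactly the arm difference at baseline, and it is estimated freely. The treatment effect is then read from beta11 and beta21: "Of particular interest are parameters that reflect the interaction between intervention condition and Time".

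The Protocol's account of procedures fixes the order of events. The survey comes first: "After participants completed the baseline survey, they were scheduled for an in-person" lab session. Allocation follows: "At the start of the lab session, participants were randomized to either a cue reactivity PFI condition or assessment-only condition".

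The only provision for precision in the SAP is optional: "We will also consider adding baseline covariates to improve precision or if evidence suggests an imbalance". It names no covariate and does not say how one would enter the model.

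**The concern.** A baseline measured before randomisation has the same expected value in both arms. Estimating beta01 spends information on a quantity that the design already sets to zero. The contrast of interest becomes the follow-up difference minus the observed baseline difference, so it carries the full chance imbalance at baseline. A model with a common baseline mean subtracts only the part of that imbalance that the baseline-to-follow-up correlation supports.

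What is at stake is precision on the very parameters the SAP singles out, in a preliminary test of a brief intervention. The validity of the comparison is not in question.

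**Working it through.** **Inputs.** The documents give no sample size, power, SD, dropout rate or correlation, so there is no stated figure to reproduce and every input below is an assumption. Let rho be the correlation between baseline and follow-up, and k the follow-up SD divided by the baseline SD (baseline SD set to 1). The relative loss does not depend on the allocation ratio.

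**Linear model, complete data.**

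- beta01 free: the variance of beta21 is proportional to 1 + k² − 2k·rho.
- beta01 = 0: it is proportional to k²(1 − rho²).
- Loss, as a share of the planned model's variance: (1 − k·rho)² / (1 + k² − 2k·rho). At k = 1 this is (1 − rho)/2.

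Worked cases:

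- k = 1, rho = 0.5: 0.25/1.00 = 25%.
- k = 0.8, rho = 0.5: (1 − 0.4)²/(1.64 − 0.8) = 0.36/0.84 = 43%.
- k = 1.2, rho = 0.7: (1 − 0.84)²/(2.44 − 1.68) = 0.0256/0.76 = 3%.

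| k | rho 0.5 | rho 0.6 | rho 0.7 |
|---|---|---|---|
| 0.8 | 43% | 40% | 37% |
| 1.0 | 25% | 20% | 15% |
| 1.2 | 13% | 8% | 3% |

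At k = 1 the standard error shortens by 1 − √(1 − loss), which is 13%, 11% and 8%. At k = 1.2 and rho = 0.8 the loss is 0.0016/0.52 = 0.3%. Three-wave generalised least squares reproduces the closed form at both follow-ups. In a simulation of the linear case (3,000 runs, 200 participants, rho 0.5) both estimators were unbiased, and the variance ratio was 0.01545/0.02049 = 0.754, against 0.75 expected.

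**Dropout.** Assume 10% miss only the 3-month survey and 10% miss both follow-ups, with k = 1 and the same rho between all waves. The loss at 3 months is then 21%, 17% and 13%.

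**Count model.** The relevant quantity is the expected Fisher information for a two-wave Poisson model with log-normal person effects, with beta01 free or fixed at 0. With baseline mean 3 or 8, log-scale SD 0.8 at both waves, no effect, and observed-count correlation 0.46 to 0.65, the loss is 18–28%. At mean 8, correlations of 0.46, 0.55 and 0.65 give 26.3%, 22.2% and 17.9%, against (1 − rho)/2 = 27%, 22.5% and 17.5%. The linear formula is therefore a fair guide if rho is the correlation of the observed counts; with the latent log-scale correlation it understates the loss. Across 48 scenarios (follow-up log-scale SD 0.70–0.95, latent correlation 0.6–0.9, with or without a 20% fall over time and a rate ratio of 0.8) the loss runs from 2% to 39%.

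**Do the optional covariates recover it?** Take the linear model with k = 1.

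- A Level 2 main effect shifts all waves equally and cancels from the within-person change. It cuts the variance of beta21 by 0% with complete data, and by at most about 4% under the dropout above.
- A covariate-by-time term cuts the variance by (r1 − r0)²/[2(1 − rho)], where r0 and r1 are the covariate's correlations with baseline and follow-up. This is 0% if r0 = r1. With r0 = 0.2 it runs from 0.09/1.0 = 9% (r1 = 0.5, rho = 0.5) to 0.16/0.6 = 27% (r1 = 0.6, rho = 0.7).
- Adding the common baseline mean to that last model leaves a variance proportional to 1 − R², with R² = (rho² + r1² − 2·rho·r0·r1)/(1 − r0²). The total cut becomes 38–52%. For example, with rho = 0.5 and r1 = 0.6, R² = 0.49/0.96 = 0.51, and the cut is 1 − 0.49/1.0 = 51%.

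**The case against.** The strongest reply is that nothing here is wrong. The planned parameterisation is valid, the study is described as preliminary, and the documents set no power or precision target that the loss could breach. That is accepted, and it is why the point is a recommended improvement and not a correction.

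A second reply is that the size is unknown and depends on the model. This also stands. The equations write three person-level random effects plus a residual for three occasions, which will probably have to be simplified. With a random intercept only and log-scale SD 0.8, the two-wave count calculation gives a loss of about 8% at mean 8 and 16% at mean 3, lower than the 18–28% above. The gain is smaller but does not vanish.

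A third reply is that the SAP already considers baseline covariates for precision. That does not meet the point: as main effects they recover essentially nothing, and the SAP specifies no interaction with time.

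Finally, craving is most naturally read as a survey outcome, since the wave labels match the surveys. That is plausible but unstated. The Protocol also collects lab questionnaires after allocation ("During the lab session, participants complete a series of questionnaires, both before and after the cue exposure"), although the arms diverge only later ("After the cue reactivity protocol, participants in the control condition complete several additional questionnaires to increase comparability of session time").

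**Conclusion.** The concern holds as a point of efficiency. Among linear cases with equal SDs and rho between 0.5 and 0.7, the planned model gives up 15–25% of its variance with complete data and 13–21% with the assumed dropout. The count-model scenarios span 2–39%. The loss is larger if the follow-up SD is below the baseline SD, and close to nil if it is above and rho is high. The algebra is firm; the size in this trial cannot be fixed from the documents, because they give neither rho nor the SDs. In the linear model the constraint never increases the variance, so for outcomes measured before randomisation there is little reason not to use it.

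**What to change.** Remove beta01 from the Level 2 intercept equation and keep r00i. The model then has a common baseline mean, with arm effects at 2 weeks and 3 months only. Apply this to every outcome whose baseline is measured before randomisation. If a zero-altered model is used, impose the constraint in both of its parts.

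State first where baseline craving is measured. If it comes from the baseline survey, the constraint applies. If it comes from the lab questionnaires, it follows randomisation, and the constraint then requires that participants did not know their arm when they answered, which the documents do not say.

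Modelling only the follow-ups, with log(baseline + 1) as a covariate, is an alternative for counts. It is not equivalent, and it drops participants who miss both follow-ups.

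The cost is SAP wording: baseline is already collected, and participants without follow-up stay in the constrained model. The Protocol describes enrolment steps in the past tense, so timing matters. If outcomes have already been examined by arm, keep the planned model as primary and report the constrained model as a labelled sensitivity analysis.
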